6.2 Duration of Study

Planned Duration for an Individual Patient

There will be a maximum 72-hour study treatment period followed by a 72-hour follow-up period.

Planned Duration for the Study as a Whole

The study will be considered completed when all patients have completed the Final Examination.

The start of the study (enrollment of first patient) is 2nd quarter 2014 and the estimated end of the study is 4th quarter 2017.

Premature Termination of the Study

Both the Investigator and the Sponsor reserve the right to terminate the study at any time. Should this be necessary, the procedures will be arranged on an individual study basis after review and consultation by both parties. In terminating the study, the Sponsor and the Investigator will ensure that adequate consideration is given to the protection of the patients' interests.

Furthermore, the Investigator should promptly inform the Independent Ethics Committee (IEC)/Institutional Review Board (IRB) and provide a detailed written explanation. The pertinent regulatory authorities should be informed according to national regulations.

Should the study be prematurely terminated, all study materials (completed, partially completed and blank CRFs, investigational product, etc.) must be returned to the Sponsor.

7 ASSESSMENTS AND METHODS

7.1 Background / Baseline Information

The following information will be captured upon enrollment:

- Physical examination with vital signs (see **Section 7.3.6**).
- Relevant Medical History including relevant prior medications (taken within 7 days prior to time 0 (study drug given)) and on-going relevant concomitant medications.

- Demographic data including height, BW, gender, date of birth, and ethnicity.
- Blood group determination.
- Blood samples for hemostatic and laboratory parameters (see **Sections 7.2.1** and **7.3.5.3**, respectively).
- Pregnancy testing for females \geq 11 years old or of childbearing potential (if younger than 11 years old).
- Type of surgical procedure indicated and use of ECMO and/or CPB

7.2 Efficacy Assessments

7.2.1 Hemostatic Parameters

The secondary objective of this study is to assess the efficacy of Octaplas in the pediatric population by measuring hemostatic parameter improvements reflecting changes in hemostasis.

The following hemostatic parameters will be assessed: INR, PT, aPTT, TEG with Kaolin activation or ROTEM EXTEM testing.

7.3 Safety Assessments

7.3.1 Relevant Drug Safety Information

Any of the following drug safety information shall be collected after the start of the first infusion episode:

- SAEs
- ADRs temporally associated with administration of the investigational product (definitions and reporting requirements see **Sections 7.3.2** and **7.3.3**)
- AEs that fall into the category of TEs, TEEs and hyperfibrinolytic events
- Post-treatment related safety reports, pregnancies, drug overdose, interaction, abuse, misuse, medication error, lack of efficacy (see **Section 7.3.7**)

Non-serious AEs observed during the trial will not be captured in the CRF (except for TEs, TEEs, and hyperfibrinolytic events as explained above).

Post-treatment, the Investigator will provide an overall Assessment of Safety observed for each patient by indicating his or her opinion of one of the following 3 categories best describing the patient's experience with treatment while on study:

- Excellent: defined as the treatment was well tolerated by the patient
- Moderate: defined as adverse drug reaction(s) were observed, but easily resolved or not clinically significant
- Poor: Defined as adverse drug reaction(s) were observed requiring significant medical intervention

7.3.2 Adverse Events and Adverse Drug Reactions

7.3.2.1 Definitions

Adverse event (AE): An AE is any untoward medical occurrence in a study patient receiving an IMP and which does not necessarily have a causal relationship with this treatment. An AE can therefore be any unfavorable and unintended sign (including an abnormal laboratory finding), symptom, or disease temporally associated with the use of an IMP, whether or not related to the IMP.

Adverse drug reaction (ADR): An ADR is any noxious and unintended response to an IMP related to any dose. The phrase “response to an IMP” means that a causal relationship between the IMP and an adverse event carries at least a reasonable possibility, i.e., the relationship cannot be ruled out.

Withdrawal due to ADR/AE: Is a patient whose treatment with IMP is discontinued because of an ADR. Any such events will be followed up by the Investigator until the event is resolved or until the medical condition of the patient is stable. All follow-up information collected will be made available to the Sponsor.

7.3.2.2 Collection

The condition of the patient will be monitored throughout the study. ADRs/AEs will be elicited using a standard non-leading question such as “How have you been since the last evaluation?” If children or adolescent patients are unable to adequately understand and respond to this question, the information will be obtained from the patient’s guardian and/or Investigator or study nurse.

Any ADR or above defined AE after the first administration of study drug which occurs during the study will be noted in detail on the appropriate pages of the CRF. If the patient reports several signs or symptoms, which represent a single syndrome or diagnosis, the latter should be recorded in the CRF. The Investigator responsible will grade the severity of all ADRs/AEs (mild, moderate or severe), the seriousness (non-serious or serious) and causality, as defined below (**Sections 7.3.2.3, 7.3.2.4, and 7.3.3**). The Sponsor is responsible to assess the expectedness of each ADR/AE (expected or unexpected), as defined below (**Section 7.3.2.4**).

Diseases, signs and symptoms and/or laboratory abnormalities already existing before the first administration of IMP are not considered as ADRs/AEs when observed at a later stage unless they represent an exacerbation in intensity or frequency (worsening).

The Investigator responsible should always provide detailed information concerning any abnormalities and the nature of, and reasons for any necessary action(s), as well as any other observations or comments, which are useful for the interpretation and understanding of the patients’ ADRs/AEs.

7.3.2.3 Severity

The intensity/severity of all ADRs/AEs will be graded as follows:

- mild: an ADR/AE, usually transient, which causes discomfort but does not interfere with the patient's routine activities;
- moderate: an ADR/AE which is sufficiently discomforting to interfere with the patient's routine activities;
- severe: an ADR/AE which is incapacitating and prevents the pursuit of the patient's routine activities.

Grading of an ADR/AE is up to the medical judgment of the Investigator and will be decided on a case by case basis.

7.3.2.4 Causality

The following causality definitions should be used for classification of each AE:

- Probable: Reports or laboratory test abnormality, with reasonable time relationship to drug intake.
Unlikely to be attributed to disease or other drugs.
Response to withdrawal clinically reasonable.
Re-challenge not required.
- Possible: Reports or laboratory test abnormality, with reasonable time relationship to drug intake.
Could also be explained by disease or other drugs.
Information on drug withdrawal may be lacking or unclear.
- Unlikely: Reports not following a reasonable temporal sequence from IMP administration. An event which may have been produced by the patient's clinical state or by environmental factors or other therapies administered.
- Not related: Reports for which sufficient information exists to conclude that the etiology is unrelated to the IMP.
- Unclassified: Reports which for one reason or another are not yet assessable, e.g., because of outstanding information (can only be a temporary assessment).

The following causality definitions should be used for classification of each ADR:

- Probable: Reports or laboratory test abnormality, with reasonable time relationship to drug intake.
Unlikely to be attributed to disease or other drugs.
Response to withdrawal clinically reasonable.
Re-challenge not required.
- Possible: Reports or laboratory test abnormality, with reasonable time relationship to drug intake.
Could also be explained by disease or other drugs.
Information on drug withdrawal may be lacking or unclear.

Classification of ADRs:

ADRs will be classified by the Sponsor as either expected or unexpected:

- expected: an adverse event that is listed in the current edition of the Investigator's Brochure (IB).
- unexpected: an adverse event that is not listed in the current edition of the IB, or that differs because of greater severity or greater specificity.

7.3.2.5 *Outcome*

The outcome of all reported ADRs/AEs has to be documented as follows:

1. recovered, resolved
2. recovering, resolving
3. not recovered, not resolved
4. recovered, resolved with sequelae
5. fatal
6. unknown

NOTE: A patient's **death** per se is not an event, but an outcome. The event which resulted in patient's death must be fully documented and reported, even in case the death occurs within four (4) weeks after IMP treatment end, and without respect of being considered treatment-related or not.

7.3.2.6 *Action(s) Taken*

ADRs/AEs requiring action or therapy must be treated with recognized standards of medical care to protect the health and well-being of the patient. Appropriate resuscitation equipment and medicines must be available to ensure the best possible treatment of an emergency situation.

The action taken by the Investigator must be documented:

- a) in general
 - none
 - medication (other than IMP) or other (e.g., physical) therapy started
 - test performed
 - other (to be specified)
- b) on IMP
 - none
 - product withdrawn
 - dose reduced
 - dose increased

The responsible Investigator will follow-up each ADR/AE until it is resolved or until the medical condition of the patient is stable and all relevant follow-up information will be reported to the Sponsor.

7.3.3 *Serious Adverse Events (SAEs)*

A **serious** AE is any untoward medical occurrence at any dose:

- results in death,
- is life-threatening (this implies that the patient was at an immediate risk of death at the time of the event, and not a hypothetical situation of what could or would have happened if, for example, no treatment had been administered),
- requires in-patient hospitalization or prolongation of existing in-patient hospitalization (hospitalization does not refer to the treatment of an ADR/AE on an out-patient status)

or to hospitalization because of study-related procedures (e.g., infusion at two consecutive days) or because of an elective surgical procedure for which the date had been scheduled earlier),

- results in persistent or significant disability/incapacity,
- is a congenital anomaly/birth defect,
- is another important medical event (e.g., suspected transmission of an infectious agent, or other reactions that should be reported in an expedited manner although they did not immediately result in one of the above seriousness criteria).

Medical judgment should be exercised in deciding whether an ADR/AE is serious in other situations. Important ADRs/AEs that are not immediately life-threatening or do not result in death or hospitalization but may jeopardize the patient or may require intervention to prevent one of the other outcomes listed in the definitions above, should also be considered serious.

SAE reporting timelines

All SAEs occurring after the start of the first infusion episode are to be reported by telephone, fax or e-mail immediately to the Clinical Project Manager (CPM) or designee. Contact details will be communicated at the study initiation visit.

7.3.4 TEs, TEEs and Hyperfibrinolytic Events

To allow continuous monitoring of the product's safety, all hyperfibrinolytic events, TEs and TEEs and other safety information as defined below must be documented and reported to Octapharma. All the above mentioned events will be reported regardless of severity or relatedness to the product. For this trial a "clinically relevant hyperfibrinolytic event" is defined by one of the following test results in the presence of a bleed that requires intervention.

1. Kaolin TEG: estimated percentage lysis (EPL) > 7.5% at 30 min (after starting assay)
2. ROTEM EXTEM: maximum lysis (ML) > 7.5% at 30 min (after starting assay)

The following list includes diagnoses and symptoms of possible TEs and TEEs that could be expected to be reported:

Acute myocardial infarction

- Increased heart enzymes*
- Electrocardiogram signs of myocardial infarction*
- Angina pectoris*
- Acute coronary syndrome*

Chest pain or pressure*
Cardiac arrest**

(Ischemic) Stroke

Transient ischemic attack

Cerebrovascular accident

Vision or speech disorders*
Unilateral paresis/weakness
Movement disorders*
Dysphasia*
Sudden severe headache*

Deep vein thrombosis

Pain or tenderness in leg(s)*
Pain in calf/calves*
Swelling calf/calves/lower legs*

Pulmonary embolism

Unexplained shortness of breath*
Sudden chest pain getting worse with a deep breath, coughing, or chest movement*
Cyanosis*

Thrombophlebitis

Infusion site thrombosis

* Possible sign or symptom of TEE

** May be outcome of TEE

To determine/confirm a TE or TEE the following adjudicators will be involved:

Adjudicator 1 (Investigator)

On the corresponding safety reporting form of the CRF, the Investigator is specifically asked if the reported event is a TE or TEE in his/her opinion.

Adjudicator 2 (Octapharma Central Drug Safety Unit, CDSU)

Once a TEE/TE is recorded on the CRF, the event will be forwarded to Octapharma's Drug Safety Unit who will process the TEE/TE in routine manner (including assessments of expectedness, causality, seriousness, TEE/TE classification of event).

Adjudicator 3 (Independent Data Monitoring Committee, IDMC)

The IDMC will receive anonymized case reports and/or lists of all reported adverse reactions. Serious cases, probably or possibly related and suspected TEEs/TEs (as determined by Adjudicator 1 and/or Adjudicator 2) will be reviewed on an ad-hoc basis; other cases like ADRs and not related SAEs will be reviewed on a quarterly basis. The IDMC will then vote on all new cases (simple majority), record their judgment and return their decisions back to data management.

In case, the adjudicators disagree, the following scheme will be applied (**Table 1**):

Table 1: Scheme of Decision for Adjudicators

Determined as TEE/TE by Adjudicator 1?	Determined as TEE/TE by Adjudicator 2?	Determined as TEE/TE by Adjudicator 3?	Determined as TEE/TE in database?
Yes	no	no	yes
Yes	yes	no	yes

No	yes	no	yes
No	no	yes	yes
No	yes	yes	yes
Yes	no	yes	yes

Abbreviations: TE=thrombotic event; TEE=thromboembolic event

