8.6 Independent Data Monitoring Committee (IDMC)

An IDMC will be established by the Sponsor. The IDMC will be composed of recognized experts in the field of hematology, transfusion medicine, immunology, pediatric surgery and/or pediatric critical care who are not actively recruiting patients.

The IDMC will review relevant quarterly safety line listings and SADR narratives periodically during the study and will give advice on the continuation, modification or termination of the study. A study specific Standard Operating Procedure will define in detail the composition, responsibilities and procedures of the IDMC.

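### Non-thrombotic deaths and life-threatening SAEs graded not related reach the IDMC only at quarterly review, with no narrative promised to it

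*Protocol*

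**What the plan says.** **Routing.** Protocol 7.3.4, under Adjudicator 3, gives the IDMC two routes. The fast one reads "Serious cases, probably or possibly related and suspected TEEs/TEs (as determined by Adjudicator 1 and/or Adjudicator 2) will be reviewed on an ad-hoc basis". The slow one reads "other cases like ADRs and not related SAEs will be reviewed on a quarterly basis". Neither singles out deaths or life-threatening events.

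**Material.** Section 7.3.4 says "The IDMC will receive anonymized case reports and/or lists of all reported adverse reactions". Section 8.6 says "The IDMC will review relevant quarterly safety line listings and SADR narratives periodically during the study". It also gives the IDMC the task of advising whether the study goes on, changes or stops, and adds: "A study specific Standard Operating Procedure will define in detail the composition, responsibilities and procedures of the IDMC". That procedure is not among the public documents.

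**Who grades causality.** Section 7.3.2.2 says "The Investigator responsible will grade the severity of all ADRs/AEs (mild, moderate or severe), the seriousness (non-serious or serious) and causality". For events recorded as thrombotic or thromboembolic, 7.3.4 adds processing by the sponsor's drug safety unit, "including assessments of expectedness, causality, seriousness, TEE/TE classification of event". SAP 11.1 lets the sponsor's medical expert, as well as the investigator, class an event as an adverse drug reaction. The causality scale for adverse events in 7.3.2.4 has five grades: Probable, Possible, Unlikely, Not related and Unclassified.

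**Rules elsewhere that ignore causality.** All SAEs go to the sponsor immediately (7.3.3). Deaths within four weeks of treatment are reported whether or not they are thought related (7.3.2.5, 7.3.7). SAP 11.1 analyses SAEs whatever their grade and plans a narrative for each death and each other serious event.

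**The concern.** The study has no control group (3.3) and no interim analysis (9.4), and the package insert states that the product has not been evaluated in children (8.4 of the insert). There is no concurrent event rate against which a causality grade could be checked, so the IDMC's own reading of serious cases is the main independent check during the trial.

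Reactions already reported with the product include circulatory overload, pulmonary edema, cardiac arrest and respiratory failure (Protocol 1.3). In children having cardiac or liver surgery, these have plausible competing explanations. If a non-thrombotic death is graded not related, the IDMC learns of it more slowly, and with less guaranteed detail, than if it is graded possible. Yet this is the kind of case in which an independent reading adds most. What is at stake is the timeliness and depth of IDMC advice on continuing the trial.

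**Working it through.** **Step 1: what each kind of serious case gets from the IDMC rules.** The plan gives no figure of its own to reproduce, so the check starts by setting 7.3.4, 7.3.2.4 and 8.6 side by side.

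| Serious case | IDMC route (7.3.4) | Narrative promised to IDMC (8.6) |
|---|---|---|
| Probable or Possible | ad hoc | yes |
| Suspected TE/TEE, any grade | ad hoc | only if it is also a SADR |
| Not related, non-thrombotic, including death | quarterly | no |
| Unlikely, non-thrombotic | not named | no |
| Unclassified, non-thrombotic | not named | not stated |

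Two points of reading:

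- The comma in the fast-route sentence could suggest that all serious cases go ad hoc. The slow-route clause rules that out, because it places not-related SAEs in the quarterly review.
- The slow route is worded by example, so Unlikely and Unclassified SAEs probably fall there by default. The text does not say so. SAP 11.1 counts reactions with missing or indeterminate causality as adverse drug reactions, but that is an analysis rule and sets no IDMC route.

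**Step 2: length of the wait.** A quarter is 365.25 / 4 = 91.3 days, which is the longest wait. If events fall uniformly within the quarter, the mean wait is 91.3 / 2 = 45.7 days. One patient's study course is at most 72 h + 72 h (+ 6 h) = 144 to 150 h, or 6.0 to 6.25 days.

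**Step 3: patients treated during the wait.** The input is 50 patients (Protocol 9.1). The two timeline sections give different starts, so both are used. Even enrolment is assumed.

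| Source | Period | Quarters | Patients per quarter | Share of 50 | Mean during half a quarter |
|---|---|---|---|---|---|
| Protocol 3.2 | Q2 2015 to Q4 2017 | 3 + 4 + 4 = 11 | 50 / 11 = 4.5 | 9.1% | 2.3 |
| Protocol 6.2 | Q2 2014 to Q4 2017 | 3 + 4 + 4 + 4 = 15 | 50 / 15 = 3.3 | 6.7% | 1.7 |

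So about 3 to 5 further patients at most, and about 2 on average, would be treated before the IDMC sees a case on the slow route. Uneven enrolment would change these figures. The narrative gap does not depend on them: it applies at every quarterly review.

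**The case against.** The strongest case against is that this is only a preference for faster review, because much already limits the damage.

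- **The check exists.** Not-related SAEs do reach the IDMC, which votes on every new case. The sponsor hears of all SAEs at once, and the trial is open-label. This stands: a reader might infer that such deaths escape independent review, and they do not.
- **The site does not hold the gate alone.** The fast-route sentence refers to Adjudicator 1 and/or Adjudicator 2, and SAP 11.1 gives the sponsor's medical expert a say. This stands in part. The parenthesis may govern only TE/TEE status, and 7.3.4 describes the drug safety unit's causality assessment only for recorded TEs/TEEs. On either reading, someone other than the IDMC sets the grade.
- **Thrombotic cases are exempt.** Suspected TEs/TEEs go ad hoc whatever their grade. This stands, and limits the point to non-thrombotic events.
- **Not related is not the default grade.** A reader might infer that competing explanations push most events there. Section 7.3.2.4 says otherwise: an event with reasonable timing that disease could also explain is Possible, and Not related needs enough information to conclude that the cause lies elsewhere. This stands. Some room for judgement remains, because Unlikely also refers to the patient's clinical state, and that grade has no named route.
- **Narratives are planned.** SAP 11.1 covers every death and serious event. This stands for the study report; nothing supplied says that the IDMC receives them.
- **Unseen material may close the gap.** The IDMC procedure is not public, the text directly after the SAE reporting timelines was not available here, and the SAP cites protocol Version 10 of 29-Nov-2017, later than the supplied protocol of 19-Nov-2016. Any of these may add detail, and nothing is inferred from their absence. Sections 7.3.4 and 8.6 as supplied still state the rule.

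**Conclusion.** The point holds in a limited form. For a non-thrombotic death or life-threatening SAE, the causality grade decides whether the IDMC reviews it ad hoc or at the next quarter, and whether a narrative to the IDMC is promised. In this respect IDMC routing is out of line with the plan's other handling of deaths and SAEs, which disregards causality. The added wait is up to about 91 days (mean about 46), with about 3 to 5 further patients treated at most and about 2 on average. That rests on 11 or 15 quarters of even enrolment and uniform event timing.

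Two stronger readings fail. A reader might infer that unseen deaths could build up over much of the trial, but one interval covers about 7% to 9% of the 50 patients. A reader might also infer that the primary SAE endpoint is compromised. It is not: SAP 11.1 counts SAEs whatever their causality, IDMC timing cannot alter that count, and the adjudication scheme in Table 1 decides only TE/TEE status. The remaining weakness lies in the speed and depth of oversight, and it is cheap to remove.

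**What to change.** 1. **Protocol 7.3.4, Adjudicator 3.** State that every death and every life-threatening SAE goes to the IDMC ad hoc, with a narrative, whatever its causality grade. Name the route for other SAEs graded Unlikely or Unclassified. Other not-related SAEs can stay quarterly. Reword the fast-route sentence so that it is clear whether the reference to the two adjudicators covers causality or only TE/TEE status.
2. **Protocol 8.6.** Extend the narratives supplied to the IDMC to *SADR, death and life-threatening SAE narratives*.
3. **IDMC procedure.** Align it with both sections. If it already covers deaths regardless of grade, bring that rule into the protocol.

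The change affects oversight only, not treatment. Narratives for deaths and serious events are already planned for the study report, but preparing them in real time for the IDMC is additional work. The cost is that earlier preparation and a few extra ad-hoc reviews by the existing committee.
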